**ClinicalTrials.gov Identifier**  
**NCT04899232**

**1) Objectives\***

This will be a prospective, randomized, open label, interventional pilot trial to test the hypothesis that deficient endogenous AT3 is associated with a prothrombotic hyperinflammatory state associated with COVID-19.

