**4) Number of Subjects\***

The study population will be comprised of 75 patients assigned to one of three groups of 25 COVID (+) patients each.

The proportion of subjects with AT3 levels < 100% will be 50/50 randomization of which 25 subjects with AT3 <100% will be standard of care and 25 subjects with AT3<100% will be standard of care with exogenous AT3 supplementation. The third group will be subjects with AT3 levels  $\geq 100\%$ .

- a. 25 patients with endogenous AT3 >100% who receive standard of care only or
- b. 25 patients with endogenous AT3 <100% who receive standard of care only or
- c. 25 patients with endogenous AT3 <100% who receive standard of care plus supplemental AT3.

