**7) Study Endpoints\***

The Primary endpoint is change from baseline in the ISTH DIC Score to Day 9.

The Secondary endpoints include change from baseline D-dimers, Fibrinogen & Prothrombin time, length of hospital stay (days), mortality (%), and Pulmonary function (including Time (days) to mechanical ventilation and/or ECMO Duration (days) of new ventilator or extracorporeal membrane oxygenation (ECMO) use, Change from baseline SOFA and SOFA Respiratory sub-score, Number of venous thromboembolisms, Number of major bleeding events

Subjects discharged prior to completion of intervention would be classified as having a successful outcome. We anticipate that all cause morbidity will occur in 10-20% of the COVID study population, despite standard of care. We anticipate that these patients will be deficient in endogenous AT3.

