## **9) Statistics\***

Statistical analyses will be performed using SPSS version 21 (IBM Corporation, Armonk, NY). Parametric data are reported as  $M \pm SD$  and nonparametric data are reported as median (interquartile range). Missing values for continuous variables are handled by applying imputation methods before calculating their statistics. The study population will be stratified into two halves based on the primary outcome of change from baseline SOFA and/or ICH DC. Those with the fastest rate of recovery are compared to those with the slowest rate of recovery. We expect that AT3 will correlate with rate of recovery and/or with one or more of the secondary outcomes. The demographics and physiologic variables in the fastest and slowest groups are compared using a t test or Mann-Whitney U-test, as appropriate. Categorical variables are compared using a  $\chi^2$  or Fisher's exact test, as appropriate. Statistical significance is determined at  $p < 0.05$ . Then multivariate models will be evaluated for predicting the primary or secondary outcomes, using various performance metrics, such as area under the receiver operating characteristic curve, sensitivity and specificity, positive predictive value, and negative predictive value, as we have described in multiple previous studies. In addition, propensity scores will be assigned for each patient based on a 1:1 fixed ratio nearest neighbor matching was performed to compare those with fastest or slowest recovery. A 1:1 fixed ratio nearest neighbor matching is performed to minimize bias without sacrificing power, as we have described in multiple previous studies.

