### Appendix C

The Secondary endpoint measurements:

- a. D-dimer level change from baseline to Day 9 in mcg/mL FEU or DDU,
- b. Fibrinogen level change from baseline to Day 9 in mg/dL
- c. Prothrombin time change from baseline to Day 9 in seconds
- d. Length of hospital stay in days,
- e. Mortality (%) of overall and between groups,
- f. Pulmonary function
  - a. Time (days) to mechanical ventilation and/or
  - b. ECMO Duration (days) or extracorporeal membrane oxygenation (ECMO) use,
- g. SOFA score change from baseline to Day 9 and
- h. SOFA Respiratory sub-score change from baseline to Day 9,
- i. Number of venous thromboembolisms from admission to hospital discharge,
- j. Number of major bleeding events from admission to hospital discharge

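### Section 9 lets recovery or any one secondary outcome agree with its expectation at an unadjusted p < 0.05, and blurs which primary outcome counts

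*Combined protocol and SAP*

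**What the plan says.** Section 7 (Study Endpoints) is clear about the primary: "The Primary endpoint is change from baseline in the ISTH DIC Score to Day 9". It lists change in SOFA among the secondary endpoints.

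Section 9 (Statistics) does not carry this through. It has the study population "stratified into two halves based on the primary outcome of change from baseline SOFA and/or ICH DC", where the last two words presumably mean the ISTH DIC score. It then compares the faster-recovering half with the slower. Its one statement of what the trial should show is "We expect that AT3 will correlate with rate of recovery and/or with one or more of the secondary outcomes". The threshold follows the comparisons of the two halves: "Statistical significance is determined at" p < 0.05.

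Appendix C, under "The Secondary endpoint measurements", gives ten lettered items, a to j, the last being "Number of major bleeding events from admission to hospital discharge". Item f has two parts, so there are 11 measurements.

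The documents give no adjustment for multiple tests, no order of testing, and no statement that any analysis is exploratory. Section 1 calls the study a "prospective, randomized, open label, interventional pilot trial" and says that it will test a hypothesis.

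**The concern.** The expectation is a disjunction. It is met by recovery alone, by any one secondary outcome alone, or by any mixture. Recovery itself can be defined on one score or on two. With one unadjusted threshold and no order among the outcomes, there are many routes to a result that agrees with the expectation, even if AT3 has no relation to any outcome.

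What is at stake is how the report can be read. A single p-value below 0.05, on a coagulation marker or on length of stay for example, would fit the sentence in Section 9 while the Section 7 endpoint showed nothing. A reader could not tell from the plan whether that result had been the basis for judgement all along.

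**Working it through.** **Inputs**

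- Per-test level: 0.05 (Section 9). Sidedness is not stated; two-sided is assumed.
- Number of outcomes: 1 for recovery plus Appendix C. This gives 1 + 10 = 11 with item f counted once, and 1 + 11 = 12 with item f split. Testing recovery separately on both scores gives 13, although this partly double-counts, since SOFA change is already item g.
- Correlation among outcomes: not given in the documents. Assumed equal for all pairs and varied from 0 to 0.9.
- Sample size: "The study population will be comprised of 75 patients assigned to one of three groups of 25 COVID (+) patients each". It does not enter the calculation below except through the size of exact tests.

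**The plan's own figure.** There is none to reproduce. The documents give no familywise error rate, power or sample-size calculation; 0.05 is simply an input.

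**Independent outcomes.** The chance of at least one p < 0.05 with no true association is 1 − 0.95^k:

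- k = 11: 1 − 0.95^11 = 43.1%
- k = 12: 1 − 0.95^12 = 46.0%
- k = 13: 1 − 0.95^13 = 48.7%

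**Correlated outcomes.** Simulation of k two-sided z-tests with a common pairwise correlation (400,000 replicates) gave:

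| Assumed correlation | k = 11 | k = 12 | k = 13 |
|---|---|---|---|
| 0.3 | 37.4% | 39.7% | 41.9% |
| 0.5 | 30.4% | 31.9% | 33.5% |
| 0.7 | 22.3% | 23.2% | 24.1% |
| 0.9 | 13.1% | 13.5% | 13.9% |

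The count of outcomes matters little. The correlation matters a good deal.

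**Conservative exact tests.** Section 9 allows Fisher's exact test for categorical data, and its true size is below 5% when events are rare. At nominal 0.05, with 25 against 25, it is 0.9% at a 10% event rate and 2.2% at 20%. For halves of 37 and 38 it is about 2.5% and 3.7%. As an illustration, suppose that 4 of the 12 outcomes (such as mortality, thromboembolism, major bleeding and ECMO use) have a true size of 1%. Under independence the chance becomes 1 − 0.95^8 × 0.99^4 = 1 − 0.6634 × 0.9606 = 36%. At correlations 0.3, 0.5 and 0.7 it is about 32%, 26% and 19%.

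**After the change.** One named test at two-sided 5% has a 5% chance of a false positive, whatever the correlation.

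**The case against.** Four points can fairly be made on the other side.

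First, a reader might infer that the plan declares the hypothesis supported as soon as any one outcome reaches p < 0.05. The documents do not say so. The sentence predicts what the investigators think they will see and is not a decision rule, and Section 7 does separate one primary endpoint from the secondaries. This stands, so the error rates above are conditional on a hit being read as support. It does not remove the problem, because Section 9 offers no other criterion and does not keep to the Section 7 endpoint.

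Second, the threshold follows the comparison of fast and slow recoverers, and no test of AT3 against each outcome is named. Applying 0.05 to every such correlation is a reasonable reading of the section but not an explicit one. This also stands.

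Third, a range such as 23% to 46% might be taken as a property of the plan. It is not. The outcomes overlap: by Appendix A the DIC score is built from platelets, D-dimer, fibrinogen and prothrombin time, the last three of which are also secondary outcomes, and SOFA contains its respiratory sub-score. Full independence is therefore unrealistic, and 46% is a ceiling for 12 outcomes with non-negative correlation. Nor is 23% a floor. Equally, length of stay, mortality, thromboembolism and bleeding are components of neither score, so a uniform 0.9 across all 12 is implausible too.

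Fourth, this is a pilot, and unadjusted exploratory testing in a pilot is defensible when labelled as such. Here the label is missing. A reader might go on to infer that a false positive would trigger a larger trial. The documents mention no subsequent trial and no go/no-go criterion, so that consequence cannot be claimed.

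**Conclusion.** The concern holds in conditional form. Section 9 combines a disjunctive expectation, one unadjusted threshold, no order or exploratory label, and a primary outcome that disagrees with Section 7. If any one hit among about 12 outcomes were taken as support, the false-positive chance would be up to 46%, and roughly 40%, 32%, 23% and 13% at correlations of 0.3, 0.5, 0.7 and 0.9. Allowing for conservative exact tests lowers these somewhat, for example from 32% to 26% at correlation 0.5.

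These figures rest on an assumed common correlation, two-sided tests, a true size of 5% unless stated otherwise, and the reading that 0.05 applies to each outcome. The exact value cannot be fixed from the documents. The direction can: the chance exceeded 5% in every case tried, and at correlation 0.9 it was still more than twice 5%.

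**What to change.** Make three edits in Section 9.

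1. Replace the sentence of expectation with a statement that the hypothesis is judged only on the Section 7 endpoint, change in ISTH DIC score from baseline to Day 9, in one named comparison at two-sided 5%. For the treatment question, that comparison is between the two randomised groups with AT3 below 100%. Naming it matters because Section 9 specifies no between-arm test and Section 1 words the hypothesis as an association with deficient endogenous AT3. Keeping both questions at 5% each would give up to 1 − 0.95^2 = 9.75% if the tests were independent.
2. Delete the description of the primary outcome as SOFA and/or a DIC score, so that Sections 7 and 9 agree and SOFA stays secondary.
3. State that the Appendix C outcomes are exploratory, reported as estimates with 95% confidence intervals, and support no claim of significance.

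No extra patients, visits or data are needed. The downside is that fewer results can be called significant.

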Thus, COVID might be a dysregulated inflammatory state superimposed on disseminated intravascular coagulation (DIC) with consumptive coagulopathy [PMID: 32302438]. These patients are at high risk for both thrombosis and bleeding, as well as an overwhelming cytokine storm. The pathogenic mechanism is not fully elucidated, but the dysregulated coagulation is probably orchestrated by inflammatory cytokines, lymphocyte cell-death, hypoxia, and endothelial damage [PMID: 32558075]. This is a project to develop an entirely novel evidence-based treatment that targets both the coagulopathy and the inflammation.

In 183 consecutive patients with COVID, the overall mortality was 11.5%. On admission, the non-survivors had higher D-dimer and fibrin degradation product (FDP) levels, longer prothrombin time and activated partial thromboplastin time compared to survivors; 71.4% of the deaths and only 0.6% survivors met the criteria of DIC [PMID: 32073213]

In 40 patients with COVID, whole blood thromboelastometry (TEM) was consistent with hypercoagulability characterized by an acceleration of blood clot formation and higher clot strength. This hypercoagulable state persists for at least 5-10 days and was associated with deep vein thrombosis in six patients (15%), thromboembolism in 2 patients (5%), and catheter-related thrombosis in 12 patients (30%). The ICU and the hospital mortality were 10% and 12.5%, respectively. [PMID: 32394236]

In 16 COVID patients, the pro-coagulant TEM profile was characterized by an increased clot strength (CS), platelet contribution to CS, fibrinogen contribution to CS elevated D-dimer levels, and hyperfibrinogenemia. Fibrinogen levels were associated with interleukin-6 values. [PMID: 32302448].

In 24 COVID patients, the R, K, Alpha, and MA TEM parameters were all consistent with hypercoagulability. Platelet count was normal or increased, prothrombin time and activated partial thromboplastin time were near normal. Fibrinogen, D-dimer, C-reactive protein, Factor VIII and von Willebrand factor, protein C were all increased whereas AT3 was decreased [PMID: 32302438]. In 94 patients with COVID vs 40 healthy controls, whereas D-dimer, fibrin/fibrinogen degradation products (FDP), and fibrinogen (FIB) in all SARS-CoV-2 cases were all higher, but AT3 was lower [PMID: 32172226].

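### Section 9 judges prediction models in 75 patients by AUC and predictive values with no stated predictor limit, validation or confidence interval; scored in the fitting sample, these figures would be inflated

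*Combined protocol and SAP*

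**What the plan says.** Section 4 (Number of Subjects) sets the size: "The study population will be comprised of 75 patients assigned to one of three groups of 25 COVID (+) patients each".

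Section 9 (Statistics) first divides the patients by recovery: "The study population will be stratified into two halves based on the primary outcome". It compares the fast and slow halves at p < 0.05, and then continues: "Then multivariate models will be evaluated for predicting the primary or secondary outcomes, using various performance metrics". The measures it names are the AUC, sensitivity, specificity, PPV and NPV. For support it refers to the investigators' previous studies. It does not give the model type, the predictors or how many there may be, a selection rule, a cut-point rule, any split sample, cross-validation, bootstrap or shrinkage, or an interval around the metrics.

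No event count is given for the models. The nearest figure is in section 7 (Study Endpoints): "We anticipate that all cause morbidity will occur in 10-20% of the COVID study population, despite standard of care". Section 2 (Background) cites mortality of 11.5% in one series of 183 patients. For another series, of 40, it says: "The ICU and the hospital mortality were 10% and 12.5%, respectively".

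**The concern.** A model scored in the patients who supplied its coefficients looks better than it is. The excess grows with the number of predictors and shrinks with the number of events. The plan leaves the first open, and for some of its outcomes the second is likely to be small.

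Section 9 expects AT3 to correlate with rate of recovery or with a secondary outcome. An uncorrected AUC in the 0.7s or 0.8s could easily be taken as support for that expectation when the model has no predictive value. A follow-on study could then be built on it.

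The median split raises a separate problem. PPV and NPV depend on how common the outcome is, and here the split itself sets that frequency.

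**Working it through.** The plan states no precision or power figure for these models, so there is nothing of its own to reproduce.

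**Expected events, N = 75**
- Section 7, 10-20% (labelled morbidity, used here as a proxy): 75 × 0.10 = 7.5 to 75 × 0.20 = 15.
- Section 2 mortality of 10%, 11.5% and 12.5%: 7.5, 8.6 and 9.4 deaths.
- Primary outcome split into halves: about 37/38.

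**Candidate predictors.** The number is not stated, so a range is assumed. For scale, the data-collection list in section 8 has eight laboratory values, besides demographics, vital signs and scores. If all eight entered a model, events per predictor would be 8/8 = 1.0, 15/8 = 1.9 and 37/8 = 4.6.

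**Null simulation.** Each run has 75 patients, a fixed number of events, independent standard-normal predictors unrelated to outcome, and a near-unpenalised logistic model, with 1,000 runs per cell. AUC = [R₁ − n₁(n₁+1)/2] / (n₁n₀), where R₁ is the rank sum of the events' scores and n₁ and n₀ count patients with and without the event. It is computed in the fitting sample. The same models applied to 2,000 new patients had a mean AUC of 0.50 in every cell.

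Mean AUC in the fitting sample (chance of reaching 0.70 or more):

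| Noise predictors | 8 events | 15 events | 37 events (split) |
|---|---|---|---|
| 1 | 0.58 (6%) | 0.56 (1%) | 0.55 (0%) |
| 2 | 0.63 (16%) | 0.60 (5%) | 0.58 (1%) |
| 3 | 0.67 (32%) | 0.63 (10%) | 0.61 (3%) |
| 5 | 0.72 (61%) | 0.68 (34%) | 0.64 (11%) |
| 8 | 0.79 (88%) | 0.72 (67%) | 0.68 (32%) |
| 12 | 0.86 (98%) | 0.78 (93%) | 0.73 (72%) |
| best 3 of 12, chosen on the data | 0.78 (90%) | 0.72 (68%) | 0.68 (30%) |

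Repeat runs move single cells by about 0.01.

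**Predictive values, rare outcomes.** With eight noise predictors and the best cut chosen in the same data, PPV is 0.32 and NPV 0.97 at 8 events, and 0.40 and 0.92 at 15 events. Calling every patient event-free already gives an NPV of 1 − 8/75 = 0.89 or 1 − 15/75 = 0.80.

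**Predictive values, split outcome.** PPV = se·π / [se·π + (1 − sp)(1 − π)], where π is the prevalence. Take the sensitivity of 0.69 and specificity of 0.66 that eight noise predictors give in the split sample, with assumed prevalences for illustration:
- π = 0.50: 0.345/(0.345 + 0.170) = 0.67
- π = 0.20: 0.138/(0.138 + 0.272) = 0.34
- π = 0.10: 0.069/(0.069 + 0.306) = 0.18

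Sensitivity and specificity are the same in all three lines. Only the prevalence changes, and in this trial the split fixes it.

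**Does bootstrap correction suffice?** With eight noise predictors, the corrected AUC averages roughly 0.60 at 8 events and 0.57 at 15 or 37 events, against a true 0.50. Correction removes most of the optimism but not all of it, so it has to be paired with few predictors.

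**The case against.** The strongest reply is that the plan does not say models will be scored in the fitting sample. It is silent, and it points to earlier work that may contain a validation step. That is fair, and it makes the conclusion conditional. It does not remove the point, because the plan describes no second cohort or split sample and a reference to other studies fixes nothing for this one.

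Four stronger readings are tempting, and the documents do not support them:
- *The models will look accurate by chance alone.* This depends on the number of predictors. With 1-2 prespecified predictors, the chance of an AUC of 0.70 or more is 6-16% at 8 events, 1-5% at 15 and 0-1% for the split.
- *The plan will use at least eight predictors.* The eight laboratory values are items to be collected, not a model specification, and PT and INR overlap. Section 9 names only AT3 as expected to matter. However, its comparison of many variables at p < 0.05 comes before the models and leaves room for data-driven selection (last table row).
- *Every model has 8-15 events.* The 10-20% is a morbidity rate, and morbidity is not a listed endpoint. It is a reasonable proxy for mortality. It does not describe the split primary outcome or continuous outcomes such as length of stay.
- *PPV and NPV will look impressive for rare outcomes.* A null PPV of 0.32-0.40 does not, and a high NPV there mostly reflects low prevalence.

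It is also true that this is a pilot and that the models are not its primary endpoint. That limits the consequence, but an exploratory label would not correct an inflated number.

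**Conclusion.** The point holds in conditional form. If the metrics are computed in the fitting sample, which the plan permits and nothing in it prevents, they will be biased upward. For outcomes with about 8-15 events, noise alone gives a mean AUC from about 0.56 (one predictor, 15 events) to 0.86 (twelve predictors, 8 events). For the median-split primary outcome the range is about 0.55 to 0.73. The inflation is therefore modest with one or two prespecified predictors and serious with many predictors or with selection on the data.

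Separately, and whatever the number of predictors, PPV and NPV for the split outcome have no clinical population to which they apply.

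These sizes assume independent predictors, the proxy event rates and a near-even split. Ties in an integer score could make the split uneven. Overlap between predictors would lower the effective number. In the other direction, platelets, PT, D-dimer and fibrinogen are components of the ISTH DIC score (Appendix A). Using them to predict change in that score would add circularity that the simulation does not count.

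**What to change.** Amend section 9 before the data are analysed:
1. Name the outcomes to be modelled and, for each, a small predictor set scaled to the expected events: AT3 plus one other for rare outcomes such as death, and somewhat more for the split outcome if justified. Alternatively, specify a penalised model. State that predictors will not be chosen from the preceding significance tests.
2. Make the bootstrap optimism-corrected AUC, with a confidence interval, the headline figure. Repeat every modelling step, including any selection, inside each bootstrap sample. Show the uncorrected AUC only beside it.
3. Drop PPV and NPV for the median-split outcome.

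This needs no further patients or data. It costs a little more analysis work, and the reported AUC will be lower and less precise.

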**8) Procedures Involved\***

Any member of the study team will discuss potential subjects with the clinical team for appropriate pursuit of informed consent and screening for eligibility.

75 eligible subjects, after consent, will have laboratory blood tests for further screening.

25 of those subjects with endogenous **AT3  $\geq$  100%** will continue with SOC.

50 of those subjects with endogenous **AT3 < 100%** will be will be randomly assigned to begin **SOC plus treatment with exogenous AT3 supplementation or only SOC** treatment. The randomization schedule will be established by a member of the study team that is not involved in the informed consent process.

They will all be followed up for laboratory blood tests, study endpoints and adverse events. If they do not meet entry criteria they will be excluded from the study.

[figure not shown]
Consented subjects will be scored according to The International Society of Thrombosis and Haemostasis Disseminated Intravascular Coagulation scale (ISTH DIC) on study visit days 1, 3, 5, 7, 9 and 11.

The SOFA score will be performed only when the parameter is obtained clinically and monitored for changes in patient status on study visit days 1, 3, 5, 7, 9 and 11. Each organ system is assigned a point value from 0 (normal) to 4 (high degree of dysfunction/failure). It will be calculated on admission and Day 11 using the worst parameters measured during the study visit day. If a parameter is not obtained clinically it will be voided for research purposes.

UM IRB# 20201048

AT3 in COVID-19  
January 24, 2022, Version 6.2

After enrollment and each 48h period (+/- 12 hours) thereafter, blood samples are collected and assayed for routine clinical coagulation and inflammation markers, including AT3 activity, D-Dimer, anti-Xa, fibrinogen, and prothrombin time until Day 11.

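### Propensity matching is applied to fast versus slow recovery, an outcome rather than an exposure, and in no variant tested does it both reduce bias and keep power

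*Combined protocol and SAP*

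**What the plan says.** Section 9 first divides all patients by their result: "The study population will be stratified into two halves based on the primary outcome of change from baseline SOFA and/or ICH DC". It compares the faster and slower halves with univariate tests. It then evaluates multivariate models by ROC area, sensitivity, specificity and predictive values. After that, "propensity scores will be assigned for each patient", and the purpose is explicit: "1:1 fixed ratio nearest neighbor matching was performed to compare those with fastest or slowest recovery". The justification is "A 1:1 fixed ratio nearest neighbor matching is performed to minimize bias without sacrificing power".

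Section 9 gives no covariates for the score, no caliper, no rule on replacement and no expected number of pairs. It names no comparison of the two randomised arms.

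On design, section 4 says "The study population will be comprised of 75 patients assigned to one of three groups of 25 COVID (+) patients each". Only patients with AT3 below 100% are randomised ("50/50 randomization of which 25 subjects with AT3 <100% will be standard of care", the other 25 also receiving AT3). Under section 8, patients at or above 100% "will continue with SOC" and are not randomised.

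**The concern.** Propensity matching makes exposed and unexposed patients comparable on measured baseline factors. In section 9 the two groups being matched are outcome groups, each of which may mix all three study groups. The score is then a prognostic model of recovery, and the matched comparison asks how AT3 differs between fast and slow recoverers. It does not ask what AT3 does to recovery.

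The sizes also conflict with the stated aim. When two groups are almost equal in size, 1:1 matching can keep nearly everyone or it can improve balance, but not both. A report that repeats the plan's sentence could therefore present a comparison as bias-controlled when it is essentially the unmatched one, or present a much smaller sample as costing no power.

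**Working it through.** **Inputs from the documents.** N = 75 in three groups of 25 (section 4). Halves of 37 and 38 if there are no ties (section 9). The primary endpoint is the change in ISTH DIC score to Day 9 (section 7). Appendix A makes that score an integer with maximum 2 + 1 + 2 + 3 = 8. The plan gives no power figure or number of pairs to reproduce.

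**Assumptions, because the plan is silent.** 1 to 10 covariates; no caliper, or 0.2 SD of the logit score; c-statistic for fast versus slow of 0.5 to 0.9; two-sided alpha 0.05. Simulations used greedy nearest-neighbour matching on a fitted logistic score, 200 runs per scenario unless stated.

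**Step 1: no caliper, no replacement.** All 37 patients in the smaller half are paired and one of 38 is dropped, so 74 of 75 stay. Dropping a patient with value x from a group of 38 with mean m gives a new mean of m + (m − x)/37. Even a patient 2 SD from the mean shifts it by only 2/37 = 0.05 SD. Simulation agrees (one covariate):
- c = 0.6: imbalance 0.40 to 0.35 SD
- c = 0.7: 0.76 to 0.71 SD
- c = 0.8: 1.22 to 1.16 SD

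A separate simulation of 400 trials let severity lower both AT3 (r = −0.5) and recovery, with no effect of AT3 itself. Severity imbalance went from 0.86 to 0.82 SD, and a false significant AT3 difference appeared in 40% of trials before matching and 38% after. The level depends on the assumed correlation: a re-run gave 11% before matching at r = −0.2 and 77% at r = −0.7.

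**Step 2: caliper of 0.2 SD.** Balance is reached (residual about 0.01 to 0.05 SD). Mean share of the 75 patients discarded:

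| Covariates | c = 0.5 | 0.6 | 0.7 | 0.8 | 0.9 |
|---|---|---|---|---|---|
| 1 | 26% | 30% | 36% | 49% | 64% |
| 5 | 31% | 33% | 41% | 51% | 68% |
| 10 | 37% | 38% | 45% | 56% | 70% |

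**Step 3: other cases.**
- Ties in an integer score can make the groups unequal. A 30/45 split without a caliper drops 15/75 = 20%.
- In 500 runs with rounded outcomes and ties placed in the fast group, the smaller group averaged 23. Then 46 of 75 are kept and 29/75 = 39% dropped. Imbalance after matching was 0.32 SD (about 0.84 with untied halves), and false AT3 significance fell from 47% to 11%.
- Matching with replacement used about 46 to 58 distinct patients, leaving 17 to 29 (23% to 39%) unused.

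**Step 4: what the loss means for power.** With n per group (independent groups, normal approximation), the effect detectable with 80% power is (1.960 + 0.842) × √(2/n), and power at effect d is Φ(d/√(2/n) − 1.96). The value d = 0.66 SD is assumed.

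| Pairs | Patients lost | Detectable effect | Power at 0.66 SD |
|---|---|---|---|
| 37 | 1 (1%) | 0.65 SD | 0.81 |
| 28 | 19 (25%) | 0.75 SD | 0.69 |
| 19 | 37 (49%) | 0.91 SD | 0.53 |
| 11 | 53 (71%) | 1.19 SD | 0.34 |

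**The case against.** The best defence is that comparing AT3 between outcome groups matched on a risk score resembles a matched case-control analysis, which can remove measured confounding. That stands. With a caliper, false AT3 significance in the re-runs fell to 3% to 7%, from 20% to 71% unmatched. A reader might infer that the matching is useless, or that a severity-driven association survives every version of it. The documents do not support that: survival is shown for the version without caliper or replacement on near-equal halves.

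A reader might also infer that matching discards almost half the patients. That cannot be derived from the plan. Losses of 41% to 49% arose at fitted c-statistics of about 0.74 to 0.81 in the one- and five-covariate runs, and the plan fixes neither the covariates nor a caliper. Nor are there only two possible outcomes, since ties and replacement give intermediate results. Comparing significance rates before and after caliper matching would also overstate the cost, because the unmatched test is inflated by confounding. For that reason step 4 uses plain power formulas.

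It would be too strong to say that the non-randomised comparison gets no modelling. Section 9 plans multivariate models, but their covariates are unstated and they are judged as predictors, so they are not a specified confounder adjustment.

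Finally, this is a pilot, and the matching is an addition to the other analyses. That lowers the priority but does not make the sentence correct.

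**Conclusion.** The point holds in this form. The propensity score is built for an outcome group, so the matching does not estimate an AT3 effect, and the claim of less bias at no cost in power fails in every variant tested. Near-equal halves without a caliper or replacement keep 37 pairs and almost all the imbalance. A caliper removes the imbalance but costs about 25% to 70% of patients. Unequal groups from ties reduced the imbalance at a loss of 39% in the case simulated.

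The 37-pair result needs only N = 75, untied halves and 1:1 matching without a caliper or replacement. The loss range rests on the assumed caliper, covariates and separation, and the power figures on an assumed effect size. The matching should be changed, but it is secondary to the outcome-split analysis it belongs to, and the two are best handled in one revision.

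**What to change.** In section 9, delete the propensity matching of fastest against slowest recovery, together with the statement that power is not sacrificed. State that the two randomised AT3 <100% arms are compared without matching, since randomisation already protects that contrast.

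For the non-randomised comparison of groups a and b (AT3 ≥100% versus <100%, both on standard of care alone), keep all 50 patients. Adjust by prespecified regression, or weight by the propensity of having AT3 <100%, using age and Day 1 ISTH DIC score, and adding Day 1 SOFA where available.

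The cost is wording only: age and the Day 1 scores are already scheduled (section 8 and Appendix B). There are two limits. Day 1 SOFA may be incomplete, because section 8 scores a component only if it was obtained clinically. And either method adjusts for measured covariates only, so the comparison of groups a and b remains observational.
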